10.2 Sample calculation and interim analysis

The sample for the primary outcome (reduction in lethality in patients with severe respiratory virus treated with a high dosage of chloroquine compared to a low dosage) was calculated based on the following assumptions:

- 3. The 20% lethality incidence in critically ill patients per year in the low dosage group;
- 4. High dosage chloroquine will be able to reduce lethality by at least 50% compared to low dosage chloroquine;

Thus, considering a test of differences in proportions between 2 groups of the same size, with power of 80% and alpha of 5%, 394 participants will be needed (197 per group). Considering 10% losses, the sample size is 440 participants.

To include interim analyses, we recalculate the sample sizes required in each of the analyzes and in the final analysis, using an alpha-spending function approach, in which the type 1 error is controlled by alpha correction final, based on the alphas used for interim analyses. There are several alpha spending functions and there is always a trade-off between how much will be 'spent' on the interim analysis and the final sample size required. In summary, the more difficult it is to reject the null hypothesis in the interim analysis, the less alpha will be spent and the impact will not be large. We will use Hwang-Shih-DeCani spending functions with $\gamma = -4$ for the upper limit (that is, to interrupt the study that rejects the null hypothesis in the interim analysis), which corresponds to a conservative method, equivalent to the upper limit of O 'Brien-Fleming, with little impact on the final sample size. We will also include a lower limit for testing futility, also using the Hwang-Shih-DeCani spending function, but with a less stringent $\gamma = -2$ parameter for a beta spending function. Although the calculation includes a possible interruption due to futility, this can be ignored, at the discretion of the DSMB (or equivalent) without any impact on the type 1 error.

The table below shows the calculations for the 3 interim analyses and for the final analysis, showing both the sample size required in each analysis as well as the upper (one-tailed 2.5%) and lower limits.

| | | | Superior Limit | | | |
|------------|---|----|----------------|--------|-----|--------------|
| Sample | | | | | | |
| size | | | | p one- | | |
| percentage | | N | Z | tailed | Z | p one-tailed |
| | | 10 | - | 0.278 | 3.1 | |
| 25% | 8 | | 0.59 7 | 6 | | 0.0008 |
| | | 21 | 0.3 | 0.638 | 2.8 | |
| 50% | 5 | 5 | 6 | 2 | | 0.0024 |
| | | 32 | 1.1 | 0.882 | 2.4 | |
| 75% | 2 | 9 | 1 | 4 | | 0.0074 |
| | | 42 | 2.0 | 0.978 | 2.0 | |
| 100% | 9 | 1 | 0 | 1 | | 0.0220 |

The procedure will be based on the calculation of the Z value of the difference of proportions test in each of the analyses, and the study will continue if this value is between the values of the lower and upper limits and will be interrupted if it is above the upper limit (by rejection H0) or below the lower limit (for futility), remembering that the latter can be ignored without prejudice to the calculations.

All calculations in this report were made in the R environment, version 3.6.1, with the functions implemented in the TrialSize and gsDesign packages. Other intermediary analyzes can be carried out throughout the study to periodically monitor the safety of participants and will provide possible prior information on treatment to the DSMB and Ministry of Health.

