1.3 Sample calculation

The sample for the primary outcome (reduction in lethality) was calculated assuming a 20% lethality incidence in critically ill patients not using CQ (historical control) and that both arms of CQ would be equally able to reduce lethality by at least 50%. Thus, considering a test of differences in proportions between 2 groups of the same size, 80% power and 5% alpha, 394 participants were needed (197 per group). Adding 10% of losses, the final sample of 440 participants was obtained. Sample calculation was performed in the R statistical package (v3.6.1), with the functions implemented in the TrialSize and gsDesign packages.

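### The 440 target adds 10% losses to the single-look 394, not to the 429 the interim design requires, so power under the plan's own assumptions is about 77% to 79%, not 80%

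*Protocol*

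**What the plan says.** Section 10.2 of the protocol takes these steps in order.

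- **Assumptions.** The low-dose death rate is given as "The 20% lethality incidence in critically ill patients per year in the low dosage group". The effect is given as "High dosage chloroquine will be able to reduce lethality by at least 50% compared to low dosage chloroquine", that is, 20% against 10%.
- **Single-look size.** For a two-proportion comparison with equal arms, the section states "with power of 80% and alpha of 5%, 394 participants will be needed (197 per group").
- **Losses.** "Considering 10% losses, the sample size is 440 participants". Section 5.1 gives the same derivation, and section 1.3 says "Adding 10% of losses, the final sample of 440 participants was obtained".
- **Interim analyses.** Only after this does the section say "To include interim analyses, we recalculate the sample sizes required in each of the analyzes and in the final analysis". It specifies Hwang-Shih-DeCani spending with γ = −4 for efficacy (one-tailed 2.5%) and γ = −2 for a beta-spending futility limit that the DSMB may ignore.
- **Table.** Looks are at 25%, 50%, 75% and 100%. The digits are split over two lines in the text version, so the last line reads "100% | 9 | 1 | 0 | 1 | | 0.0220". Joined with the line above it, this gives N = 429, Z = 2.01 and p = 0.0220. The earlier rows give N = 108, 215 and 322.

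The target remains 440 in sections 1.2 and 4.1, and the randomisation list in section 7 has 110 blocks of 4, which is also 440.

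**The concern.** Section 10.2 contains two sample-size calculations that are not joined. The first gives 394 for one look and adds losses to reach 440. The second gives 429 for four looks and adds nothing for losses. The trial adopts the target from the first and the stopping boundaries from the second.

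The stated 80% power for the primary outcome therefore belongs to a design without interim analyses. A reader weighing a non-significant result would rely on a power figure that the adopted combination of looks, losses and enrolment does not quite reach.

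**Working it through.** **Inputs (section 10.2):** 20% vs 10%; two-sided alpha 5% (one-sided 2.5%); power 80%; equal groups; losses 10%; target 440; looks at 25/50/75/100%; Hwang-Shih-DeCani γ = −4 for efficacy; γ = −2 for futility with beta 0.20, non-binding.

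**1. Reproduce 394.** Unpooled normal approximation:

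n per group = (0.20×0.80 + 0.10×0.90) × (1.960 + 0.842)² / 0.10² = 196.2, rounded up to 197; 2 × 197 = 394. This matches.

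**2. Reproduce 440.** 394 / (1 − 0.10) = 437.8, so 438, rounded up to 440. The target is therefore the single-look size plus losses.

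**3. Reproduce 429.** The boundaries were recomputed by recursive numerical integration over four equal looks.

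| Look | Upper Z | One-tailed p | Lower Z | Lower p |
|---|---|---|---|---|
| 25% | 3.155 | 0.0008 | −0.587 | 0.2787 |
| 50% | 2.818 | 0.0024 | 0.355 | 0.6386 |
| 75% | 2.439 | 0.0074 | 1.186 | 0.8821 |
| 100% | 2.014 | 0.0220 | 2.014 | – |

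These agree with the table after rounding. The maximum size exceeds the single-look size by a factor of 1.0873, and 394 × 1.0873 = 428.4, so 429. This supports reading the split cells as 429 and shows that the figure is an analysed number with no loss allowance.

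**4. Apply the stated losses to the stated target.**

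- Analysable: 440 × 0.90 = 396.
- Shortfall against the table: 429 − 396 = 33.
- Losses at which 440 still yields 429: 1 − 429/440 = 2.5%.
- Enrolment giving 429 after 10% losses: 429 / 0.90 = 476.7, so 477.

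**5. Power for 20% vs 10% with the plan's boundaries.** The drift is (1.960 + 0.842) × √(N/394).

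| Analysed N | Futility followed | Futility ignored |
|---|---|---|
| 396 (440 less 10%) | 76.8% | 79.4% |
| 429 | 80.1% | 82.5% |
| 440 (no losses) | 81.0% | 83.4% |

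Using the unrounded single-look size (392.4) as reference, the 396 row becomes 77.0% and 79.5%. Binomial simulation at 396 gives 77.5–77.6% with futility followed and 79.9–80.0% with it ignored. With efficacy boundaries alone, 403 analysable participants are needed (394 × 1.0216 = 402.5), or 448 enrolled with 10% losses.

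**6. Type I error.** If losses are proportional, the looks fall at 99/198/297/396, which are still 25/50/75/100% of the final number, so the tabulated bounds hold. If the looks were instead taken at 108/215/322 with a final analysis at 396 and unchanged bounds, the one-sided type I error with futility ignored would be 0.0244, below the nominal 0.025.

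**The case against.** The strongest reply has three parts.

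- **The futility limit is not binding.** Section 10.2 says twice that it may be ignored. With only the efficacy looks in force, power at 396 is 79.4%, and simulation puts it at 79.9–80.0%, which is 80% for practical purposes. This stands, and it is why two power figures should be given. It does not remove the point: stopping below the lower limit is the stated procedure, ignoring it is an option, and the 429 was computed with futility included.
- **Actual losses may be well below 10%.** The outcome is death by day 28, and the notes to the schedule in section 1.12 provide for telephone assessment after discharge. At losses of 2.5% or less, 440 is enough. This is plausible, but 10% is the protocol's own assumption and nothing in it argues for a lower one.
- **The shortfall is modest.** It is 0.6 to 3.2 points analytically and at most about 2.5 points by simulation. This stands and limits the severity.

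A reader might go further and infer that the information fractions are wrong and the final boundary invalid because 429 would not be reached. The documents do not support that. Looks are set as percentages of participants, proportional losses leave those percentages unchanged, and even looks at the tabulated interim numbers leave the test slightly conservative.

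**Conclusion.** The point holds as an arithmetic inconsistency: 440 is 394 plus 10% losses, while the design adopted needs 429 analysable participants. Under the plan's own assumptions (20% vs 10%, 10% losses, 440 randomised), power is about 77% if futility stops are followed and about 79% if they are ignored. The stated 80% holds at 440 with both boundaries in use only if losses do not exceed 2.5%.

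The result rests on reading the split final row as 429, which the reproduced boundaries and inflation factor support, and on the normal approximation. Simulation gives figures up to about 0.8 points higher.

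It would be too strong to say that 80% power is out of reach with the interim analyses and 10% losses, or that enrolment must rise to 477. With futility ignored the design comes within a point of 80%, and correcting the statement of power is sufficient. Type I error is not affected. Severity: minor to should-fix.

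**What to change.** In sections 1.3, 5.1 and 10.2, do one of the following.

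- State that the group-sequential design needs 429 analysable participants, and that 440 randomised with 10% losses leaves 396, giving about 77% power with the futility limit followed and about 79% with it ignored. Both figures should appear.
- Keep 80% power at 440, and replace the 10% allowance with one of 2.5% or less, justified from how day-28 vital status will be ascertained.

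Either is a change of wording and needs no extra patients; the first costs a slightly lower stated power. Raising enrolment to 477 would also reconcile the figures, at the cost of 37 more participants, but the point does not require it. Recomputing the final boundary from the spending function at the number actually analysed is optional good practice, not a correction of an error.

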11. SUPPORTING DOCUMENTATION AND OPERATIONAL CONSIDERATIONS

11.1 Regulatory, ethical and supervisory considerations of the study

This study will be conducted in accordance with the principles set out in The Belmont Report: Ethical Principles and Guidelines for the Protection of Human Research and ICH E6 (R2).

The protocol will be submitted to CONEP, via Plataforma Brasil, in accordance with the regulations established by CONEP under COVID-19.

11.2 Informed consent process

Informed consent is a process initiated before an individual agrees to participate in a study and continues throughout the individual's participation. Investigators or the designated research team will obtain informed consent from the research subject. Participants will receive a concise and focused presentation of key information about the clinical trial, verbally and with written consent. The main information about the study will be organized and presented in layman's terms and language that makes it easier to understand why someone may or may not want to participate.

The Informed Consent Term (ICF) will be approved by CONEP and the subjects must read and review the consent. The subjects (or legally authorized representatives) must sign the ICF before starting any study procedures that are being done specifically for this study. Once signed, a copy of the ICF will be given to the study subject.

Stored samples will be labeled with bar codes to maintain confidentiality. Identifiable data can occur as needed; however, confidentiality will be maintained as described for this protocol and with the approval of CONEP.

The samples will not be used for commercial purposes. Although the results of any future research may be patentable or commercially profitable, the subjects will have no financial interest in any commercial development resulting from future research.

There are no direct benefits for the individual. No secondary research results will be entered in the subject's medical record. Incidental findings will not be shared with the subject, including medically actionable incidental findings, unless required by law.

Individuals can withdraw permission to use samples for secondary use at any time. He/she will need to contact the study site and the samples will be removed from the study's biorepository.

11.3 End and termination of study

This study may be terminated prematurely if there is sufficient reasonable cause, including but not limited to:

- 1. Determination of unexpected, significant or unacceptable risks to subjects;
- 2. Results of the interim analysis;
- 3. Insufficient compliance with protocol requirements;
- 4. Data that is not sufficiently complete and / or cannot be evaluated;
- 5. Regulatory authorities decisions

If the study ends prematurely, the site PI will promptly inform the study subjects and CONEP, as applicable. The PI will ensure adequate follow-up of subjects, as needed.

11.4 Confidentiality and privacy

Confidentiality must be strictly maintained by participating investigators, and their staff. This confidentiality is extended to cover information relating to individuals, results of biological sample tests and genetic tests and all other information generated during participation in the study.

Information about the study subjects will not be disclosed to any unauthorized third party.

The confidentiality of the subject's personal information will be maintained when the results of the study are published or discussed.

The study monitor, other authorized sponsor representatives, CONEP representatives and/or regulatory agencies can inspect all necessary documents and records maintained by the investigator, including, but not limited to, medical records (office, clinic or hospital) and

pharmacy records of subjects of this study. The clinical study team will allow access to these records.

All source records, including electronic data, will be stored in secure systems in accordance with institutional policies and federal regulations.

All study data and research samples that leave the study site (including any data transmission) will be identified only by a coded number linked to a subject through a code maintained at the clinical site. Names or IDs will not be released unless the security monitoring committee approves and aligns with consent or in accordance with the laws for the required reports.

11.5 Secondary use of samples and stored data

Secondary Research in Human Subjects is the reuse of identifiable data or biospecimens collected from some other "primary" or "initial" activity, such as the data and samples collected in this protocol. Any use of samples or data for secondary research purposes, however, will be presented in a separate protocol for approval by CONEP.

Each sample will be identified only with a barcode and a unique tracking number to protect the confidentiality of the subject's personal information.

11.6 Clinical monitoring

Monitoring of the clinical site is carried out to ensure that the rights and well-being of individuals in the study are protected, that reported study data is accurate, complete and verifiable. Clinical Monitoring also ensures that the conduct of the study is in compliance with the currently approved protocol/amendment (s), ICH, GCP and the applicable regulations, requirements and sponsor's requirements. Clinical monitoring will also verify that any critical study procedures are completed following specific instructions in the protocols.

Details of clinical site monitoring are documented in a clinical monitoring plan (CMP). The CMP describes in detail who will carry out the monitoring, how often the monitoring will be carried out and the distribution of the monitoring reports.

Monitoring visits will include, but are not limited to, review of regulatory files, accountability records, CRFs, Informed Consent Forms, medical and laboratory reports, onsite study on intervention storage records, training records and protocol compliance and GCP.

Monitors will have access to each study site, participant, study personnel and all documentation in accordance with the monitoring plan (to be carried out after CONEP approval).

Study monitors will meet with investigators to discuss any outstanding issues and documentary issues.

11.7 Data management and record keeping

Data collection is the responsibility of the clinical study team under the supervision of the PI 1. The PI must keep the documentation complete and accurate.

Clinical research data and source documentation (including, but not limited to, AE/SAE, concomitant medications, medical history, physical assessments, laboratory data) will be entered by the clinical study location personnel on the CRFs.

The data system includes password protection and internal quality checks, such as automatic range checks, to identify data that appears to be inconsistent, incomplete or inaccurate.

Retention of study records and study-related records, including regulatory filing, drug registration, consent forms, source documents and electronic records must be kept for a period of 2 years after the study closure date. These documents must be retained for a longer period, however, if required by local authorities.

Data recorded in the CRF and derived documents must be consistent with the data recorded in the source document.

11.8 Protocol deviations

A protocol deviation is any non-compliance with the clinical trial protocol. Noncompliance can be on the part of the subject, the investigator or the team of the study site. After a deviation, corrective actions must be developed and implemented promptly. All individual protocol deviations will be addressed in the subject's study records.

It is the responsibility of the PI and site personnel to use continuous surveillance to identify and report deviations within five working days after the protocol deviation is identified.

All deviations must be reported immediately according to the protocol deviation reporting procedures.

Protocol deviations must be sent to CONEP, according to their guidelines.

11.9 Data publishing and sharing policy

To avoid premature release of data, this protocol specifies that the efficacy data for a study that has not yet been completed due to insufficient enrollment should not be published.

An independent monitoring committee will review the results of an interim analysis of study data to make recommendations on whether the study should continue or not.

It is important to note that investigators will remain blind to any analysis results; study data will only be released if the trial is interrupted based on a recommendation from the monitoring committee or has reached its target number of outcomes or amount of follow-up from participants.

11.10 Conflict of interest policy

The independence of this study from any real or perceived influence, such as by the pharmaceutical industry, is fundamental. Therefore, any real conflict of interest of people who have a role in the design, conduct, analysis, publication or any aspect of this test will be disclosed and managed.

11.11 Amendments to the clinical study protocol

All appendices to this document and those indicated here are part of this clinical study protocol. The investigator shall not modify or alter the clinical study protocol without prior analysis and CONEP's written approval/favorable opinion of an amendment, except when necessary to rule out immediate risk to patients in the clinical study, or when the change involves only logistical or administrative aspects of the study.

Any changes that are be agreed must be registered in writing, and the written amendment must be signed by the investigator and filed with this clinical study protocol. Any amendment to the clinical study protocol requires prior written approval/favorable opinion from CONEP, prior to its implementation, unless there are priority security reasons.

In some cases, an amendment may require a change to the Informed Consent Form. The researcher must receive approval / favorable opinion from CONEP, regarding the revised Free and Informed Consent Term, before the change is put into practice.

